8 B) SCHEDULE OF ASSESSMENTS AND MEASURES

Table 4. Schedule of procedures for study for groups 1 and 2

Attendance No.	1	2	3	4	5	6	7	8
Visit	Screening	Vaccination Visit	Follow Up 1	Follow Up 2	Follow Up 3	Follow Up 4	Follow Up 5	Follow Up 6
Timeline (days)**	<30	0	Day 2	Week 1 (Day 7)	Week 2 (Day 14)	Week 4 (Day 28)	Week 8 (Day 56)	Week 20 (Day 140)
Time window (days)			± 1	± 1	± 2	± 7	± 7	± 7
Informed consent	х							
Review contraindications, concomitant medication, inclusion and exclusion criteria	x	х						
Vaccination		х						
Vital signs ^	х	х	х	х	х	х	х	
Ascertainment of adverse events ***		х	х	х	х	х	х	х
Diary cards provided		х						
Diary cards collected						х		
Telephone Contact								х
Crohn's disease activity assessments	х						х	
Medical history	х							

Physical examination	х	х	(x)	(x)	(x)	(x)	(x)	
Biochemistry, Haematology (ml)	8	8	8	8		8		
Exploratory immunology (ml)		20				20	20	
Exploratory microbiology (ml)		10				10	10	
Urinalysis	х							
Urinary β-HCG (women only)	х	х						
HLA typing (ml)		4						
HBsAg, HCV Ab, HIV serology (ml)	5							
SARS-CoV-2 swab test	х							
Total blood volume per visit (ml)	13	32	8	8	0	28	20	0

(X) = if considered necessary $^* = Vital$ signs includes pulse, blood pressure and temperature; \$ = Biochemistry will include Sodium, Potassium, Urea, Creatinine, Albumin and Liver function tests. £ = Exploratory immunology includes ex vivo ELISPOT responses to interferon gamma ** Timeline is approximate only. Exact timings of visits relate to the day on enrolment, i.e., each visit must occur at indicated number of days after enrolment ± time window. *** Redness and swelling will be assessed by the clinical team following vaccination at days 0, 2 and 7.

Table 5. Schedule of procedures for study groups 3 and 4

Attendance No.	1	2	3	4	5	6	7	8
Viola	Canaanina	Vaccination	Follow	Follow	Follow	Follow	Follow	Follow
Visit	Screening	Visit	Up 1	Up 2	Up 3	Up 4	Up 5	Up 6
Timediae (dove)**	<30	0	Day 2	Week 1	Week 2	Week 4	Week 8	Week 12
Timeline (days)**				(Day 7)	(Day 14)	(Day 28)	(Day 56)	(Day 84)

Time window (days)			± 1	± 1	± 2	± 7	± 7	± 7
Informed consent	х							
Review contraindications, concomitant medication, inclusion and exclusion criteria	х	х						
Vaccination		х						
Vital signs ^	х	х	х	х	х	х	х	
Ascertainment of adverse events ***		х	х	х	х	х	х	х
Diary cards provided		х						
Diary cards collected						х		
Telephone Contact								х
Crohn's disease activity assessments	х						х	
Medical history	х							
Physical examination	х	х	(x)	(x)	(x)	(x)	(x)	
Biochemistry, Haematology (ml)	8	8	8	8		8		
Exploratory immunology (ml)								
Urinalysis	х							
Urinary β-HCG (women only)	х	х						
HLA typing (ml)		4						
HbsAg, HCV Ab, HIV serology (ml)	5							
SARS-CoV-2 swab test	х							

Total blood volume per visit (ml)	13	12	8	8	0	8	0	0

(X) = if considered necessary * = Vital signs includes pulse, blood pressure and temperature; \$ = Biochemistry will include Sodium, Potassium, Urea, Creatinine, Albumin and Liver function tests. £ = Exploratory immunology includes ex vivo ELISPOT responses to interferon gamma. ** Timeline is approximate only. Exact timings of visits relate to the day on enrolment, i.e., each visit must occur at indicated number of days after enrolment ± time window *** Redness and swelling will be assessed by the clinical team following vaccination at days 0, 2 and 7.

Table 6. Schedule of procedures for study Group 5

Attendance No.	1	2	3	4	5	6	7	8	9	10	11	12	13
Visit	Screenin	Vaccinatio n Visit	Follow Up	Follow Up	Follow Up	Follow Up	Boost Visit	Follow Up	Follo w Up 7	Follo w Up 8	Follo w Up 9	Follo w Up 10	Follo w Up 11
Timeline (days)**	<30	0	2	7	14	28	56	58	63	70	84	112	140
Time window (days)			± 1	± 1	± 2	± 7	± 7	± 1	± 1	± 2	± 7	± 7	± 7
Informed consent	х												
Review contraindication s, concomitant medication, inclusion and exclusion	x	х											

criteria													
Vaccination		х					х						
Vital signs ^	х	х	x	х	х	х	х	х	х	х	х	х	
Ascertainment													
of adverse		х	x	x	x	x	x	x	х	х	х	х	х
events ***													
Diary cards		х					x						
provided		^					^						
Diary cards						х					х		
collected						^					^		
Telephone													х
Contact													^
Endoscopy	х											х	
Crohn's disease													
activity	x						x					х	
assessments													
Medical history	х												
Physical		v	(x)	(x)	(x)	(x)	v	(x)	(x)	(x)	(x)	(x)	
examination	Х	X	(*)	(*)	(*)	(*)	x	(*)	(*)	(*)	(*)	(*)	
Biochemistry,													
Haematology	8	8	8	8		8	8	8	8		8		
(ml) \$													

Exploratory immunology (ml)	10	30				20	30				20	30	
Urinalysis	х												
Urinary β-HCG (women only)	х	х					х						
HLA typing (ml)		4					4						
HBsAg, HCV Ab,													
HIV serology	5												
(ml)													
SARS-CoV-2	· · · · · · · · · · · · · · · · · · ·												
swab test	X												
Total blood													
volume per visit	23	42	8	8	0	28	42	8	8	0	28	30	
(ml)													

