3.2.2 Primary outcome measures

To define the Maximum Tolerated Dose (MTD) of ChAdOx2 HAV and MVA HAV in patients with active Crohn's disease on no current immunosuppressive therapy when administered alone and in a prime-boost regimen. The definition of MTD is defined as per the Group Holding Rules in section 3.2.3.

The following parameters will be used to assess response and safety for all study groups:

- Occurrence of local reactogenicity signs and symptoms for 7 days following the vaccination
- Occurrence of systemic reactogenicity signs and symptoms for 7 days following the vaccination
- Occurrence of adverse events for 28 days following the vaccination
- Change from baseline for safety laboratory measures
- Occurrence of serious adverse events during the whole study duration

Participants in groups 1-2 will undergo clinical follow up for a further 20 weeks following completion of the vaccination regimen. SAEs will be collected throughout the study.

Participants in groups 3-4 will undergo clinical follow-up for a further 12 weeks following completion of the vaccination regimen. SAEs will be collected throughout the study. Participants in group 5 will undergo clinical follow-up for a further 20 weeks following completion of the vaccination regimen. The duration of follow up reflects the desire to obtain sufficient safety data with the first use of ChAdOx2 HAV, MVA HAV and a prime-boost regimen with ChAdOx2 HAV-MVA HAV in humans with Crohn's Disease. Considering the pre-existing safety data on several other MVA based constructs, participants receiving MVA HAV will be followed by a shorter period.

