The prime vaccination with ChAdOx2 HAV of group 5 participants will take place on day 0 and the boost vaccination of MVA HAV on day 56, for all participants.

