6.1 Analysis of primary endpoint

Determining the Maximum Tolerated Dose (MTD) for ChAdOx2 HAV will depend on the response of patients in Group 1 and 2. As stated in the Group Holding rules, if 2 or more participants in Group 2 experience Grade 3 SAR lasting more than 48 hours, then the previously tolerated dose will be recorded as the MTD. If 2 or more participants in Group 1 experience Grade 3 SAR lasting more than 48 hours, then the trial will be put on hold pending an internal safety review.

If less than 2 participants in Group 2 experience the outcome stated above, then participants in Group 3 and 4 will be subject to the same criteria for the two doses of MVA HAV. If 2 or more participants in Group 4 experience Grade 3 SAR lasting more than 48 hours, then the previously tolerated dose will be recorded as the MTD. If 2 or more participants in Group 3 experience Grade 3 SAR lasting more than 48 hours, then the trial will be put on hold pending an internal safety review.

Once the MTDs for ChAdOx2 HAV and MVA HAV is determined, then participants in Group 5 will be subject to these doses. If 2 or more participants in Group 5 experience Grade 3 SAR lasting more than 48 hours, then the trial will be put on hold pending an internal safety review.

The proportion of all individuals per group who experience Grade 3 SAR lasting more than 48 hours at the end of follow-up will be estimated with a 95% exact confidence interval. The number with expected and unexpected AEs and all SAEs will be presented alongside, according to the sample table below:

Table 6 Summary of adverse events by Group

Number experiencin experiencin g Grade 3 enrolled SAR lasting more than 48 hours Proportion experiencin g Grade 3 SAR lasting more than 48 hours (95% CI)	Number of expected local reactogenicit y signs and symptoms for 7 days following the	Number of expected systemic reactogenicit y signs and symptoms for 7 days following the	Number of unexpected adverse events for 28 days following the vaccination	Number of serious adverse events during the whole study duration
---	--	---	---	--

		vaccination	vaccination	
Group 1				
Group 5				

The median and range of values of safety laboratory measures will be plotted by group at baseline (vaccination visit) and 7 days post vaccination.

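### In Group 5 the boost may move by 7 days but the visits after it may not, so in-window post-boost safety visits can miss days 2 and 7 after the boost, or precede it

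*SAP*

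**What the plan says.** Section 4.4 places "the boost vaccination of MVA HAV on day 56, for all participants", and section 4.7 puts the two vaccinations 8 weeks apart. Neither mentions a window.

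Table 6 in section 8 B) does. From Follow Up 4 onwards its nominal days are "28 56 58 63 70 84 112 140", where day 56 is the boost visit. The windows are ± 7 for the boost, ± 1 for day 58 (Follow Up 6), ± 1 for day 63 (Follow Up 7), ± 2 for day 70 (Follow Up 8) and ± 7 for the later visits. Safety bloods are drawn at the boost and on days 58, 63 and 84, but not on day 70.

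The timeline row is marked with a double asterisk. Under Tables 4 and 5 that note calls the timeline approximate, then requires that "each visit must occur at indicated number of days after enrolment ± time window". The note belonging to Table 6 is not in the text at hand.

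The visits after each vaccination serve these purposes:
- Clinical assessment: "Redness and swelling will be assessed by the clinical team following vaccination at days 0, 2 and 7" (note under Tables 4 and 5).
- Primary outcome measure, section 3.2.2: "Occurrence of local reactogenicity signs and symptoms for 7 days following the vaccination".
- Laboratory summary, section 6.1: values are "plotted by group at baseline (vaccination visit) and 7 days post vaccination".
- Holding rules, section 3.2.3: for groups 1-5, laboratory events count if they begin within 7 days of vaccination.

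Section 5.4 reports visits outside their window as protocol deviations.

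**The concern.** In Groups 1-4 the only vaccination is on day 0, so counting visits from enrolment is the same as counting them from vaccination. Group 5 differs because its second vaccination has a 15-day window. If the later visits stay tied to enrolment with ± 1 day, their distance from the boost changes with every day the boost moves.

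Two things follow. A site that keeps to the schedule can collect post-boost safety data at the wrong time, and in some cases before the boost. A site that sees the participant 2 and 7 days after a shifted boost may have to record deviations. Group 5 is the only prime-boost group (n = 10), and prime-boost safety is part of the primary objective.

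**Working it through.** **Inputs** (Table 6): boost day b from 49 to 63 (56 ± 7, 15 permitted days); Follow Up 6 on days 57-59; Follow Up 7 on days 62-64; Follow Up 8 on days 68-72; Follow Up 9 on days 77-91. Enrolment is taken as day 0, the day of the prime. The enrolment anchor printed under Tables 4 and 5 is assumed to apply to Table 6.

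**Formula.** Days after the boost = visit day − b. For Follow Up 6 the range is 57 − b to 59 − b; for Follow Up 7, 62 − b to 64 − b; for Follow Up 8, 68 − b to 72 − b.

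**The intended timing is reproduced first.** With b = 56, Follow Up 6 falls at +1 to +3, Follow Up 7 at +6 to +8 and Follow Up 8 at +12 to +16. This mirrors the post-prime visits on days 2 ± 1, 7 ± 1 and 14 ± 2, so the intended targets after the boost are +2 ± 1 and +7 ± 1.

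**Across the permitted boost days:**

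| Boost day | Follow Up 6 (bloods) | Follow Up 7 (bloods) | Follow Up 8 (no bloods) |
|---|---|---|---|
| 49 | +8 to +10 | +13 to +15 | +19 to +23 |
| 53 | +4 to +6 | +9 to +11 | +15 to +19 |
| 54 | +3 to +5 | +8 to +10 | +14 to +18 |
| 56 | +1 to +3 | +6 to +8 | +12 to +16 |
| 58 | −1 to +1 | +4 to +6 | +10 to +14 |
| 59 | −2 to 0 | +3 to +5 | +9 to +13 |
| 60 | −3 to −1 | +2 to +4 | +8 to +12 |
| 63 | −6 to −4 | −1 to +1 | +5 to +9 |

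**Results.**
- *Follow Up 6 wholly before the boost:* this needs 59 − b < 0, so b = 60 to 63, which is 4 of 15 days.
- *No visit at +1 to +3:* the first visit after an early boost is Follow Up 6, on day 57 at the earliest. 57 − b > 3 gives b = 49 to 53, which is 5 of 15 days.
- *No safety bloods at +6 to +8:* for b = 59 to 63, Follow Up 7 comes no later than 64 − 59 = +5. Follow Up 8 has no bloods, and Follow Up 9 comes no earlier than 77 − 63 = +14. That is 5 of 15 days.
- *Both visits able to meet their own target:* the Follow Up 6 range must overlap +1 to +3 and the Follow Up 7 range must overlap +6 to +8. Both hold for b = 54 to 58 only, which is 5 of 15 days.
- *Spread of the nominal day-7 laboratory value:* Follow Up 7 runs from 62 − 63 = −1 to 64 − 49 = +15 days relative to the boost.
- *Extremes for the 7-day laboratory holding rule:* with b = 49 no scheduled post-boost bloods fall on days 1-7. With b = 63 the only ones possible in that period are on day +1.

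Follow Up 7 can precede the boost in one combination only (boost on day 63, visit on day 62). Follow Up 8 and later visits always follow the boost.

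**The case against.** The strongest reply is that the enrolment-based note is not shown under Table 6. It is printed under the two tables for single-vaccination groups, where it does no harm, and Group 5 may have its own wording. This stands as a limit on confidence: that the note carries over is an inference from the shared marker. The remark that the timeline is approximate helps less, because the same sentence group goes on to make the windows mandatory.

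The text also sets the boost at day 56 for everyone, and for boosts close to that day the schedule works. That stands too. No distribution of boost days is given, so a reader should not infer that all 10 participants are affected, or that any share of the 15 days is a probability.

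A reader might infer that on the 10 boost days outside 54-58 no visit of any kind falls 2 ± 1 or 7 ± 1 days after the boost. The schedule does not support that. For boosts on days 49-53, Follow Up 6 can land at +6 to +8, with bloods. For boosts on days 59-63, Follow Up 7 can land at +1 to +3, also with bloods. For boosts on days 60-63, Follow Up 8 can land at +6 to +8, without bloods. What is lost is one of the two checks, not both.

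A reader might also infer that the primary endpoint is compromised. Section 6.3 measures the Grade 3 endpoint over the whole of follow-up, and diary cards are issued at the boost visit and collected on day 84. Neither depends on the day-58 or day-63 window.

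**Conclusion.** The inconsistency holds, with moderate confidence, on the assumption that the note under Tables 4 and 5 also governs Table 6. A ± 7 boost window followed by ± 1 visits on the same enrolment clock keeps the intended +2 and +7 timing within reach on only 5 of the 15 permitted boost days. On each of the other 10, either the day-2 visit (boost on days 49-53) or the day-7 safety bloods (boost on days 59-63) cannot be obtained in window.

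The damage is confined to staff-assessed redness and swelling on days 2 and 7, the 7-day laboratory summary in section 6.1, and the laboratory input to the 7-day holding rule. How many participants are touched depends on how far actual boosts stray from day 56, which the document does not say.

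**What to change.** 1. Check the wording of the note to Table 6. Then reconcile the boost window, the windows of the visits after it and the enrolment anchor, so that post-boost safety visits are timed relative to the actual boost date and a correctly timed one is not a deviation under section 5.4.
2. In sections 6.1 and 6.2, define the Group 5 post-boost analysis windows from the actual boost date. State in 6.1 whether the 7-day laboratory value for Group 5 refers to the prime, the boost or each.
3. Reconcile any knock-on effect on total duration. Section 4.9 gives 20 weeks from enrolment, whereas section 3.2.2 counts Group 5 follow-up from completion of vaccination. The anchor chosen for the last visits bears on both.

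The cost is a wording change in the schedule and its note, plus one visit-window derivation in the analysis code. No extra visits or participants are needed.
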